3.0 Objectives

The proposed 4-year, multisite, randomized effectiveness-implementation trial will focus on the real-world application of bCBT for Veterans with depression, as applied by frontline CBOC practitioners. Effectiveness-implementation designs seek to simultaneously test: 1) strategies to improve care practices (e.g. clinician support programs) and 2) examine patient outcomes associated with the clinician program being implemented. The current project will invite mental health clinicians at the Houston and Oklahoma City CBOCs (16 sites) to participate. As part of study participation, providers will receive bCBT training and support from the study. Once trained, these CBOC clinicians will be asked to provide care to a Veteran patient population identified by the study team. Veteran participants from each respective CBOC, identified by study-based screening, will be randomized to a bCBT direct referral arm or to an Enhanced Usual Care (EUC) condition. Direct referral participants will be assigned to a CBOC provider trained by the study team in the use of bCBT. The study will pair providers and patients at each CBOC facility. EUC participants will not receive a direct referral. Rather, these participants will receive depression education materials, a note placed in their medical record indicating the presence of depression, and encouragement to seek services from their existing providers.

Aim 1 – Implementation (training and assisted use of bCBT by frontline CBOC clinicians): The study will use a formal evaluation procedure to capture information on the clinical and implementation efforts as delivered by CBOC providers. Data will be used to modify the clinical training and support program. Known as a formative evaluation, the study will include a developmental assessment to collect data on clinician adoption, intervention fidelity, and individual interviews with stakeholders to obtain a deeper understanding of implementation challenges associated with using bCBT in the CBOC setting.

Aim 2 – Clinical Effectiveness (patient outcomes): To determine whether depression (PHQ-9 and Beck Depression Inventory) and quality-of-life (SF-12) differ as a function of bCBT referral (vs. EUC) at 4-, 8- and 12-month follow-ups.

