Depression: Depression will be assessed using the Patient Health Questionnaire – 9 (PHQ-9) and the Beck Depression Inventory – Second Edition (BDI-II). Treatment response will be defined by a 50% reduction in depressive symptoms on both the PHQ-9 and BDI-II.³³⁻³⁵ The PHQ-9 consists of the depression module from the larger, self-administered version of the PRIME-MD⁴⁴ and is particularly versatile in its ability to assess both symptoms as well as each of the nine *DSM-V* depression criteria.³⁶ For this study, a PHQ-9 cutoff score of 10 or greater will be used for inclusion criteria. Note: The PHQ-9 will be administered by study RAs and independent evaluators as part of all “study-based assessments” and will also be used by bCBT clinicians as part of their regular course of treatment with bCBT participants. The BDI-II, a 21-item self-report instrument, will be used as a second measure of depressive symptoms. The BDI-II is psychometrically strong⁴⁵ and is reliable, internally consistent, and valid for use in the primary care setting.⁴⁶ The BDI-II will serve as a second measure of depression and, unlike the PHQ-9, will be administered exclusively by study staff.

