5.6 Data Analysis

Sample Size and Power Calculations:

Provider Sample (Implementation Data; Aim 1)

No formal sample size calculations were used for the implementation-focused elements of this project. Rather, the team will invite all CBOC providers at all sites within the HOU and OKC VAMCs to participate and subsequently evaluate how many providers opted to engage in the bCBT project. These procedures are common for implementation-focused trials that often have a smaller pool of “subjects”. Designs of this nature often look less at statistical significance and

instead focus more on descriptive quantitative data and depth interviewing and qualitative analyses to determine impact and “lessons learned”.

Veteran Sample (Effectiveness Data; Aim 2)

Sample-size calculations indicate that 232 patients will need to be randomized to address the primary hypothesis for aim 2. Based upon our current project, we will need to recruit 300 Veterans. Approximately 30% of recruited participants were screened ineligible due to subthreshold anxiety and/or depression scores.

We will use unequal randomization to reduce unnecessary recruitment, resulting in 138 patients for bCBT and 94 for EUC. In determining the sample size, we first determined the number of participants needed to have 80% power to detect significant differences in the primary outcomes between our groups. We then inflated this to account for intraclass correlations among patients and for attrition and loss to follow-up. A sample size of 70 patients in both the bCBT and EUC groups (140 total) is needed to detect a difference in the means of the primary outcome that reflects a small effect size of .30, using a 2-sided *t*-test with 80% power at the .05 significance level, adjusted for repeated measures.⁵⁶ The small effect size was chosen to ensure an adequate sample size to address multiple study aims and outcomes. The bCBT sample size was then inflated by $[1 + (m - 1) c]$ to account for the intraclass correlation due to clustering of patients within bCBT clinicians.⁵⁷ Based on the sample size of 70 bCBT patients, an average of 5.8 patients per therapist, and an assumed correlation, *c*, among patients of .10,⁵⁷ our inflation factor is 1.48 ($70 \times 1.48 = 104$). A clustering inflation factor was not used for the EUC group. Both the bCBT and EUC groups are inflated to account for attrition rate at 12 months of 25%.

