Aim 2 will determine whether depression and quality of life outcomes differ as a function of the intervention at posttreatment, and at 8- and 12-month follow-ups. All analyses will be done on an intention-to-treat basis. Following the recommendation of the CONSORT group, we will not test for differences in baseline characteristics or adjust subsequent analyses for any variables we did not decide a priori to include in the regression models.⁶³ To compare changes between the 2 groups over time, we will use a longitudinal, mixed-model analysis containing terms for the intercept, treatment, time period and interaction between time and treatment. Separate models will be run for each outcome (PHQ-9, BDI, SF-12 PCS and MCS) and for the combined outcome of whether or not the patient responded to treatment as measured by both a 50% reduction in PHQ-9 and BDI-II. Linear regression will be run for the continuous outcomes and logistic regression will be used for the combined depression outcome. We will include the use of antidepressant medications, receipt of outpatient mental health care, the modality of treatment (e.g., telephone, in-person, combination), and the stratification variable, site, in the analyses to control for any possible differences that might exist between the treatment arms that might impact our outcomes. The interaction between time and treatment will indicate whether there is a difference over time between the 2 groups. We will conduct sensitivity analyses to evaluate whether the reasons for loss to follow-up at the various time periods are related to the observed values of the outcome variable, using tests for missing completely at random and tests for nonrandom missingness.⁵⁶

Analyses for Aim 2 will occur exclusively at the Houston HSR&D CoE under the direction of the PI ([name]), study statistician (Co-I [name]), and study data analyst ([name]).

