Other analyses: Prediction of bCBT Treatment Response: We will use multivariate analyses to predict treatment response in the bCBT group, defined as 50% or greater reduction in PHQ-9 and BDI scores from baseline to posttreatment. Variables will include patient demographic and clinical characteristics (e.g., baseline depression severity, mental health comorbidities, treatment expectancy), as well as treatment (number of sessions attended, therapeutic alliance, patient engagement) and clinician factors (e.g., clinician adherence/skillfulness). Depression Treatment Intensity: Within the bCBT treatment group, the study team will evaluate the associations between depression-symptom response and treatment intensity (number of sessions). We will explore potential patient demographic and clinical characteristics associated with treatment response and intensity. Further, we will use surveys and qualitative interviews

with clinicians and bCBT participants to more fully understand whether the treatment intensity received was the treatment believed to be ideal. Perspectives from both patients and providers will be needed to fully understand this construct.

All exploratory analyses will occur exclusively at the Houston HSR&D CoE under the direction of the PI ([name]), study statistician (Co-I [name]), and study data analyst ([name]).

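### The only term given a role in comparing the arms in Aim 2 is the time-by-treatment interaction, which cannot show a steady benefit on the 50%-reduction responder outcome

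*Combined protocol and SAP*

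**What the plan says.** Section 3.0 sets Aim 2 as finding out whether depression and quality of life "differ as a function of bCBT referral (vs. EUC) at 4-, 8- and 12-month follow-ups". The sample-size text in Section 5.6 derives 70 patients per arm, described as "needed to detect a difference in the means of the primary outcome that reflects a small effect size of .30".

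The Aim 2 analysis text in Section 5.6 specifies a longitudinal mixed model "containing terms for the intercept, treatment, time period and interaction between time and treatment". It is run separately for PHQ-9, BDI, SF-12 PCS and SF-12 MCS, and also "for the combined outcome of whether or not the patient responded to treatment as measured by both a 50% reduction in PHQ-9 and BDI-II". For that last outcome, "logistic regression will be used for the combined depression outcome". On how the arms are to be judged from these models there is one sentence: "The interaction between time and treatment will indicate whether there is a difference over time between the 2 groups".

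Section 5.5 defines the binary outcome: "Treatment response will be defined by a 50% reduction in depressive symptoms on both the PHQ-9 and BDI-II". The Aim 2 text gives no visit for it. The only definition of response tied to a time is in the exploratory prediction analysis, where it is "defined as 50% or greater reduction in PHQ-9 and BDI scores from baseline to posttreatment". That analysis is confined to the bCBT arm.

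**The concern.** A time-by-treatment interaction answers Aim 2 only if one level of time precedes treatment. The arms should then agree at that level, and a later separation appears as an interaction. The responder outcome has no such level, because nobody can have a 50% reduction from baseline at baseline. Over three follow-up visits the interaction asks whether the odds ratio at 4 months differs from that at 8 or 12 months. If bCBT doubles or triples the odds of response and the benefit lasts, the interaction is null.

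Taken as written, the plan would usually read a steady responder benefit as no difference. Otherwise the deciding contrast would be chosen later, possibly after outcomes have been seen.

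**Working it through.** **1. The plan's own sample size.** Inputs from Section 5.6: effect 0.30 SD, two-sided 0.05, 80% power, 70 per arm, 5.8 patients per therapist, intraclass correlation 0.10, 25% attrition.
- Clustering factor: 1 + (5.8 - 1) × 0.10 = 1.48.
- bCBT: 70 × 1.48 = 103.6; 103.6 / 0.75 = 138.1, so 138.
- EUC: 70 / 0.75 = 93.3, so 94. Total 232, as stated.
- The base of 70 cannot be traced to one contrast. Unadjusted, n = 2 × (1.96 + 0.8416)² / 0.30² = 174.4, so 175 per arm. An average of three visits with correlation 0.10 gives 174.4 × (1 + 2 × 0.10) / 3 = 69.8. A single-visit change score with correlation 0.80 gives 174.4 × 2 × (1 - 0.80) = 69.8. The plan does not say which calculation was used.
- Effective sizes after attrition and clustering: 138 × 0.75 / 1.48 = 69.9 and 94 × 0.75 = 70.5, so about 70 per arm.

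**2. Responder interaction, by algebra.** Write L4, L8 and L12 for the log odds ratios at the three visits. The interaction tests L4 = L8 = L12 (2 df). If all three equal the same value, that hypothesis is true whatever the value, and a valid test rejects at its 5% level. This step needs no assumed response rate.

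**3. Responder outcome, by simulation.** The documents give no response rates, so these are assumptions: 20% EUC response at each visit, 70 effective patients per arm, and latent within-patient correlation 0.5 to 0.7. Odds of 0.25 times 2, 2.5 or 3 give bCBT response of 0.50/1.50 = 33.3%, 0.625/1.625 = 38.5% or 0.75/1.75 = 42.9%. Wald tests were applied to the visit-specific log odds ratios in 10,000 trials per setting.

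| Constant odds ratio | Interaction | Average of 3 visits | 4 months only |
|---|---|---|---|
| 2.0 | 5% | 59-67% | 41% |
| 2.5 | 5% | 84-90% | 65% |
| 3.0 | 5% | 95-98% | 82% |

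Repeat runs with separate code agree to within 1 to 2 percentage points.

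Hand check of the 4-month column at odds ratio 2.5: variance = 1/(70 × 0.20 × 0.80) + 1/(70 × 0.385 × 0.615) = 0.0893 + 0.0603 = 0.1496, SE 0.387. Then ln 2.5 / 0.387 = 0.916 / 0.387 = 2.37, and power is Φ(2.37 - 1.96) = 66%.

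**4. How far the 5% extends.**
- EUC response 15-30% with latent correlation 0.3-0.7: interaction 4.2-5.2%.
- EUC response rising 15/20/25%, odds ratio 2.5: interaction 4.7%, average 88%.
- 138 and 94 patients: interaction still about 5%.
- A benefit that changes can show. Odds ratios 3, 2, 1.2 give interaction 43%, average 58%, 4 months 82%.

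**5. Continuous outcomes.** With baseline as a level of categorical time, the interaction coefficients are the between-arm differences in change at each visit. For a sustained difference of d SD, compound symmetry with correlation ρ and 70 per arm, the joint 3-df test has noncentrality (70/2) × (3/4) × d² / (1 - ρ). At d = 0.30 and ρ = 0.5 this is 35 × 0.75 × 0.09 / 0.5 = 4.725, giving 42% power. Power is 24% at ρ = 0.1, 65% at 0.7 and 83% at 0.8. For a sustained 5-point PHQ-9 difference (5 / 6.1 = 0.82 SD) it is 97% even at ρ = 0.1. If baseline is not a level of time, a constant difference is again flagged only 5% of the time.

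**The case against.** The quoted sentence can be read as a correct description of an interaction rather than a decision rule. It does not say that no other contrast will be examined. The treatment term is in the fitted model. With a constant odds ratio and no interaction, its coefficient estimates that log odds ratio under any usual coding of time, and only its precision changes. The sample-size text of the same section is built on a between-arm difference in means, and the aim itself implies comparisons at each visit. The responder visits are unstated, so the 5% figure rests on one reading of the model. The stated primary outcome is depression symptoms, not response.

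Much of this stands. What is missing is a named contrast, not data or a model, and it would be wrong to infer that Section 5.6 contains no treatment comparison at all. But the analysis text gives the treatment term no role, and the one term it does give a role cannot answer Aim 2 for this outcome. The single-visit reading does not rescue it, because one visit has no interaction. The posttreatment definition belongs to an exploratory analysis within one arm, so it does not fix the visit for the arm comparison.

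A reader might also infer that the trial is underpowered for PHQ-9, BDI-II or SF-12. The documents do not support that. They give neither the correlation nor the contrast behind the repeated-measures adjustment, and the plan's stated purpose of comparing change over time is consistent with baseline being a level of time.

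**Conclusion.** The point holds for the responder outcome. If it is modelled at 4, 8 and 12 months, the interaction flags a constant odds ratio about 5% of the time, whatever its size. If one visit is meant, the stated inference cannot be applied. Under the assumed rates, the treatment contrast has about 60-98% power averaged over visits or about 40-84% at 4 months, for odds ratios of 2 to 3.

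The 5% depends on the three-visit reading, on a benefit constant on the odds-ratio scale, and on the 0.05 level from the sample-size text. The power figures depend on the assumed response rates and correlation. They allow for clustering and attrition only through the effective sample size, and include no covariates.

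For the continuous outcomes the point is conditional. With baseline as a level of time the interaction coefficients address Aim 2, and no shortfall is shown. Without it, the same defect applies. This should be fixed before analysis.

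**What to change.** In the Aim 2 analysis text of Section 5.6:
- **Responder outcome:** state the visit or visits, and make the bCBT-EUC treatment contrast (odds ratio) the test of benefit. Choose it before unblinded outcome data are analysed.
- **Reporting:** give the 4-, 8- and 12-month differences with 95% confidence intervals. Keep the interaction to describe change or decay, which Section 5.5 says is of interest.
- **PHQ-9, BDI-II and SF-12:** state whether baseline is a level of time. If it is, say whether the interaction coefficients are judged jointly or singly. If it is not, name a treatment contrast here too.
- **Sample size:** state which contrast and correlation the 80% refers to.

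Whether to use the average or a named visit is the sponsor's choice, and it is a trade-off. On the continuous scale with correlation 0.5 and baseline adjustment, a benefit fading 0.30, 0.20, 0.10 SD gives the average 45% power and the 4-month contrast 54%. One growing 0.15, 0.30, 0.45 SD gives 79% and 18%.

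The cost is wording only, with no new patients or data. Naming the contrast may show less favourable power than the stated 80%: for a sustained 0.30 SD at correlation 0.5, a baseline-adjusted single visit has about 54% and the average about 79%.

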Exploratory Aims: A) To predict bCBT treatment response, using patient, treatment, and clinician variables. B) To explore patient and provider reactions to variable-length treatment options, using outcome data, patient and provider surveys, and qualitative interviews. C) To assess stakeholder (Veterans, clinicians, clinic managers/directors, as well as regional and national VA mental health leaders) perceptions of potential for wider implementation and maintenance of bCBT poststudy, using qualitative interviews and focus groups.

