Variable Length of Treatment (see Figure 1): Clinicians will provide bCBT with a flexible treatment intensity and duration, based on an innovative model described by Galovski et al.²³ In the current study each Veteran's depressive symptoms will be assessed, using an a priori PHQ-9 outcome benchmark of 50% reduction in baseline symptoms³³⁻³⁵ to determine treatment response and to provide guidance to clinicians and patients about the potential for treatment discontinuation. Clinicians are encouraged to talk about discontinuation prior to treatment completion to 1) ensure that patients continue to see value in the treatment and wish to continue the treatment 2) explore additional or alternative treatment options that may be more in line with patient needs and/or expectations. Ideally, patients will continue with the bCBT intervention but some may elect to explore other treatment options.

PHQ-9 data will inform treatment progress but will not dictate treatment discontinuation. Rather, clinicians and patients will decide on the final length of treatment (up to the maximum 9 sessions in 4 months). A response of 50% reduction in depressive symptoms was chosen, based on prior work and evidence from other studies.³³⁻³⁵ This response criterion also appropriately classifies responders with variable depression levels. A decrease in symptoms by 50% for an initial PHQ-9 of 10 (the lowest possible entry score) would require a 5-point change (the minimally clinically important difference for the PHQ-9).³⁶

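### Exploratory Aim A names only a yes/no joint 50% response as its outcome, which discards information in the PHQ-9 and BDI-II scores already collected

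*Combined protocol and SAP*

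**What the plan says.** Section 3.0 states exploratory Aim A as "To predict bCBT treatment response, using patient, treatment, and clinician variables". Section 5.6 (Other analyses) carries it out with multivariate analyses "to predict treatment response in the bCBT group, defined as 50% or greater reduction in PHQ-9 and BDI scores from baseline to posttreatment". No further model is named there, and no continuous outcome is given for the prediction work.

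The rule is joint. Section 5.5 (Effectiveness Measures) says "Treatment response will be defined by a 50% reduction in depressive symptoms on both the PHQ-9 and BDI-II". The Aim 2 text in section 5.6 says the same, and adds that "logistic regression will be used for the combined depression outcome".

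For Aim 2 the plan keeps the scores as well: "Separate models will be run for each outcome (PHQ-9, BDI, SF-12 PCS and MCS) and for the combined outcome". Table 3 schedules PHQ-9 and BDI-II at baseline and at 4, 8 and 12 months.

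Section 5.1 (Variable Length of Treatment) explains the criterion: "A response of 50% reduction in depressive symptoms was chosen, based on prior work and evidence from other studies". It adds that the criterion suits patients with different starting severity. At the lowest entry score of 10, a 50% fall equals a 5-point change, which the plan treats as the minimal clinically important difference.

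The sample is unequal, "resulting in 138 patients for bCBT and 94 for EUC", and allows for an "attrition rate at 12 months of 25"%. No power, expected response rate or correlation between the two scales is given for Aim A.

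**The concern.** A cut at 50% on both scales treats very different patients alike and similar patients differently. A fall in PHQ-9 from 24 to 13 is 11 points, or 46%, and counts as non-response, the same as worsening. A fall from 10 to 5 meets the PHQ-9 half of the rule. A patient who improves by 60% on one scale and 45% on the other also counts as a failure.

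Aim 2 is protected because the continuous scores are modelled next to response. Aim A has no such companion analysis, and it rests on a single arm. What is at stake is the chance of detecting patient, treatment and clinician factors that do relate to outcome, and the precision of their estimates. This concerns the scale of the outcome only, not which predictors enter or when they are measured.

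**Working it through.** **Inputs from the plan (section 5.6).** 138 bCBT patients randomised; 25% attrition at 12 months; two-sided 0.05; PHQ-9 SD 6.1. The 80% power is stated for the Aim 2 arm comparison and is borrowed here only as a benchmark.

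**Assumed, because the plan is silent.** Response rate (10% to 50%), correlation between the scales (0.6 to 0.8), and the strength of the predictor.

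**1. The plan's own sample figure.** Inflation factor 1 + (5.8 - 1) x 0.10 = 1.48. Then 70 x 1.48 = 103.6, taken as 104. Dividing by 0.75 gives 138.7 for bCBT (plan: 138) and 70/0.75 = 93.3, so 94, for EUC (plan: 94). The figures reproduce within rounding. For Aim A, 138 x 0.75 = 103.5, so about 104 patients if the 12-month attrition already applied at 4 months. The 4-month number therefore lies between 104 and 138.

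**2. Loss from one cut.** If a normally distributed outcome is cut so that a proportion p respond, a predictor's correlation with it is multiplied by k = phi(z_p)/sqrt(p(1-p)). The share of information kept is k². Power for a predictor that has 80% on the continuous score is Phi[(1.960 + 0.842) x k - 1.960].

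| Response rate | k | k² | Power on yes/no outcome |
|---|---|---|---|
| 10% | 0.585 | 0.34 | 37% |
| 20% | 0.700 | 0.49 | 50% |
| 30% | 0.759 | 0.58 | 57% |
| 40% | 0.789 | 0.62 | 60% |
| 50% | 0.798 | 0.64 | 61% |

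At 20%, for example: 0.2800/0.4000 = 0.700, and Phi(2.802 x 0.700 - 1.960) = Phi(0.00) = 50%. Between 20% and 40% response, 38-51% of the information is discarded.

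**3. Check with the noncentral t distribution.** At n = 104 a correlation of 0.27 has 81% power on the score. After the cut (correlation k x 0.27) power is 49%, 56% and 60% at 20%, 30% and 40% response.

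**4. Dependence on the benchmark (same method, 20-40% response).**

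| n | Correlation | Score | Yes/no |
|---|---|---|---|
| 104 | 0.20 | 54% | 30-37% |
| 104 | 0.35 | 96% | 72-83% |
| 138 | 0.27 | 90% | 61-72% |

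Absolute power moves with the predictor's strength and n. The information ratio k² does not.

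**5. The joint two-scale rule, by simulation at n = 104, scale correlation 0.6-0.8.**

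| Joint response rate | Yes/no power when one scale has about 80% | Yes/no power when the mean of both scales has about 80% |
|---|---|---|
| 10% | 34-40% | 32-33% |
| 20% | 52-53% | 44-46% |
| 30% | 58-61% | 51-55% |
| 40-50% | 61-67% | 54-58% |

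**6. Bounded scores with baseline PHQ-9 of at least 10.** A baseline-adjusted linear PHQ-9 model had 79-82% power. The joint logistic model had 31%, 47%, 59% and 63% at response rates of 8%, 16%, 29% and 40%.

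From a starting point of about 80%, no scenario put the yes/no outcome above about two-thirds.

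**The case against.** **The criterion has a clinical basis.** A reader might infer that the cut is unsupported, or serves only to guide when treatment ends. The documents do not support that. Section 5.1 ties it to a 5-point change at the entry threshold and to fair classification across severity levels, and section 5.5 adopts it as an outcome definition with citations. That justifies reporting response. It does not deal with the efficiency lost when response is the only prediction outcome.

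**The aim is to predict response.** Section 3.0 says so, and replacing response with a score would change the question. For baseline severity, which section 5.6 names as a predictor, a model adjusted for the same scale's baseline mainly describes how baseline tracks follow-up, not who improves proportionally. This objection stands. The response model should stay in full, and the score models should be added to it.

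**The size rests on assumptions.** This also stands. The 80% start and the response rates are not in the plan, and working step 4 shows that other choices move the absolute figures. A flat statement that predictors would be found only half the time goes beyond the documents.

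**The analysis is exploratory and claims no power.** True, and the primary comparison is untouched. But Aim A is a named aim in one arm, where information is scarcest, and the scores are already collected.

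**The treatment-intensity analysis is not clearly dichotomised.** Correct. Section 5.6 speaks there of symptom response without repeating the 50% rule. The wording is ambiguous, and one cannot say that this analysis uses the cut.

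**Conclusion.** The point holds as a loss of efficiency in an exploratory analysis. It is not an error in Aim 2. Section 5.6 gives Aim A one outcome, the joint yes/no response, and does not use the full scores for prediction.

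Under the stated assumptions, a predictor with 80% power on the continuous score falls to about 50-60% at response rates of 20-40%. It falls to about one-third at 10%, and reaches at most about two-thirds at 40-50%. The power levels depend on the chosen benchmark. The relative loss from a single cut depends on the response rate and on approximate normality of the score.

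Two stronger readings are tempting and do not follow. Real predictors will not necessarily be reported as absent; they will more often be missed. Null results will not become uninterpretable: odds ratios with intervals remain readable, only less precise, and the plan sets no rule for selecting predictors by significance.

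**What to change.** In section 5.6, under Prediction of bCBT Treatment Response:

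- Add linear models of the 4-month PHQ-9 score, adjusted for baseline PHQ-9, with BDI-II handled the same way in parallel, as the main test of predictors. The mean of the two standardised scores is an acceptable alternative.
- Keep the joint 50% response model alongside, to answer the response question posed in section 3.0. Report baseline severity from that model too, and note that its coefficient in a baseline-adjusted score model means something different.
- State that the treatment-intensity analysis also uses the continuous scores, which removes the ambiguity there.

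The cost is a few sentences, with no new data, patients or assessments. The downsides are small: coefficients in scale points, which some readers find less direct than odds of response, and a second set of models to report. Nothing here bears on how the criterion is used to guide treatment length.
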